### **Nivolumab and Ipilimumab Dose Delays**

Below are dose delay and management tables for nivolumab and ipilimumab, indicating when study drug should be held or discontinued due to nivolumab or ipilimumab –specific adverse events.

ALL OTHER EVENTS	Management/Next Dose for Nivolumab and Combination Nivolumab/ipilimumab
≤ Grade 1	No change in dose. Continue treatment.
Grade 2	Hold until ≤ Grade 1 OR baseline (exceptions as noted below)
Grade 3	Off nivolumab/ipilimumab therapy. For immune-related adverse events, hold nivolumab and ipilimumab until ≤ Grade 1 OR baseline; resume at the same dose level (exceptions as noted below).
Grade 4	Off nivolumab and ipilimumab therapy (exceptions as noted below)

Recommended management: As clinically indicated

- Any adverse event, laboratory abnormality, or intercurrent illness which, in the judgment of the investigator, presents a substantial clinical risk to the subject with continued study drug dosing should discontinue nivolumab/ipilimumab treatment.
- Any grade 2 drug-related uveitis or eye pain or blurred vision that does not respond to topical therapy and does not improve to Grade 1 severity within the re-treatment period OR requires

systemic treatment should discontinue nivolumab/ipilimumab treatment.

- Any grade 3 or 4 drug-related laboratory abnormality or electrolyte abnormality, that can be managed independently from underlying organ pathology with electrolyte replacement, hormone replacement, insulin or that does not require treatment does not require discontinuation.
- Patients requiring > two dose delays for the same event should go off protocol therapy. Patients may be dose-delayed for evaluation and restarted depending on results.
- Please note that grading and for hypophysitis with symptoms of headache, visual or neurologic changes or radiologic evidence of pituitary enlargement and other CNS events such as aseptic meningitis or encephalitis should be considered grade 3 events.

Skin Rash and Oral Lesions	Management/Next Dose for Nivolumab and Combination Nivolumab/ipilimumab
≤ Grade 1	Continue therapy. No change in dose.*
Grade 2	Monitor weekly until 1≤ Grade. May initiate intermediate potency topical steroids (and treatment for pruritis if needed). Resume at same dose level.
Grade 3	Hold* until ≤ Grade 1. Resume at same level at investigator discretion.
Grade 4	Off nivolumab and ipilimumab treatment.

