
*Patients with purpuric or bullous lesions must be evaluated for vasculitis, Steven-Johnson syndrome, TEN, and autoimmune bullous disease including oral lesions of bullous pemphigus/pemphigoid. Pruritus may occur with or without skin rash and should be treated symptomatically if there is no associated liver or GI toxicity. Note skin rash typically occurs early and may be followed by additional events particularly during steroids tapering.
	
Recommended management: see Skin AE management algorithm ( Appendix C )	

Diarrhea/ Colitis	Management/Next Dose for Nivolumab and Combination Nivolumab/ipilimumab
≤ Grade 1	Continue therapy. No change in dose.
Grade 2	Hold until baseline. Treat symptomatically, and restart if improved to baseline or grade 1 at investigators discretion. No change in dose. If worsening or no improvement at 4 weeks or documented colitis by colonoscopy permanently discontinue and initiate steroid treatment.
Grade 3	Discontinue nivolumab/ipilimumab therapy. Obtain colonoscopy, and treat symptomatically
Grade 4	Discontinue nivolumab/ipilimumab therapy. 
 
Patients with grade 2 symptoms but normal colonoscopy and biopsies may be retreated after resolution.
 
Patients who require steroids should be taken off nivolumab/ipilimumab treatment.
 
Please evaluate pituitary function prior to starting steroids if possible without compromising acute care.
 
Evaluation for all patients for additional causes includes C. diff, acute and self-limited infectious and foodborne illness, ischemic bowel, diverticulitis, and IBD.
 

Recommended management: see GI AE management Algorithm ( Appendix C )	

GI: Nausea/Vomiting	Management/Next Dose for Nivolumab and Combination Nivolumab/ipilimumab
≤ Grade 1	Continue therapy. No change in dose.
Grade 2	Hold pending evaluation for gastritis duodenitis and other immune adverse events or other causes. Resume at same dose level after resolution to ≤ Grade 1.
Grade 3	Hold pending evaluation until ≤ Grade 1. Resume at same dose level. If symptoms do not resolve within 7 days, patients should discontinue nivolumab/ipilimumab treatment.
Grade 4	Off nivolumab/ipilimumab treatment.
Patients with grade 2 or 3 N-V should be evaluated for upper GI inflammation and other immune related events.	

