Liver Function: AST, ALT, Bilirubin	Management/Next Dose for Nivolumab and Combination Nivolumab/ipilimumab
≤ Grade 1	Continue therapy. No change in dose.
Grade 2	Hold until grade 1 or baseline. Resume at same dose level.
Grade 3	Discontinue nivolumab or nivolumab/ipilimumab treatment and monitor with twice weekly LFTs until Grade ≤ 2. Initiate steroid therapy.
Grade 4	Off nivolumab and nivolumab/ipilimumab therapy.

 
Continued treatment of active immune mediated hepatitis may exacerbate ongoing inflammation. Holding drug to evaluate LFT changes and early treatment are recommended.
 
	
Recommended management: see Hepatic AE management algorithm ( Appendix C )	

Pancreatitis Amylase/Lipase	Management/Next Dose for Nivolumab and Combination Nivolumab/ipilimumab
≤ Grade 1	Continue treatment. No change in dose.
Grade 2	Continue at current dose level. More frequent monitoring of lipase and amylase. Patients who develop symptomatic pancreatitis should have nivolumab/ipilimumab held if applicable and steroid treatment initiated if clinically indicated.
Grade 3	Hold until ≤ Grade 2. Resume at same dose level if asymptomatic. Patients who develop symptomatic pancreatitis should be taken off nivolumab/ipilimumab treatment. 
 
Monitor lipase and amylase once or twice weekly.
 
Optional radiographic evaluation if there is new onset of symptomatic pancreatitis. Continue at the current dose level or interrupt per investigator's discretion.
 

Grade 4	Hold until ≤ Grade 2. Resume at same dose level if asymptomatic. Patients who develop symptomatic pancreatitis should be taken off

Pancreatitis Amylase/Lipase	Management/Next Dose for Nivolumab and Combination Nivolumab/Ipilimumab
	
nivolumab and ipilimumab treatment.
 
 
• Monitor lipase and amylase once or twice weekly.
 
• Optional radiographic evaluation if there is new onset of symptomatic pancreatitis or new onset of DM
 
 
Patients who develop symptomatic pancreatitis should be taken off treatment.

For treatment management of symptomatic pancreatitis, please follow the Hepatic Adverse Event Management Algorithm ( Appendix C )	

Renal	Management/Next Dose for Nivolumab and combination Nivolumab/Ipilimumab
≤ Grade 1	No change in dose.
Grade 2	Hold until ≤ Grade 1. Resume at same dose level.

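### The Grade 3 amylase/lipase cell in Section 6.1 requires a hold, or withdrawal if pancreatitis is symptomatic, and then lets dosing continue at the investigator's discretion

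*Combined protocol and SAP*

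**What the plan says.** The nivolumab and ipilimumab dose-delay tables in Section 6.1 assign an action to each toxicity grade. In the Pancreatitis Amylase/Lipase table, the Grade 3 cell contains three statements that bear on dosing:

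- It opens with "Hold until ≤ Grade 2. Resume at same dose level if asymptomatic".
- It continues: "Patients who develop symptomatic pancreatitis should be taken off nivolumab/ipilimumab treatment".
- Its last bullet makes imaging optional when symptomatic pancreatitis is newly present, and then ends with a sentence that begins "Continue at the current dose level or interrupt per" and leaves the choice to the investigator.

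The Grade 4 cell repeats the hold, the resumption condition, the withdrawal of symptomatic patients and the optional imaging. It has no sentence allowing treatment to continue.

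In the Diarrhea/Colitis table, the Grade 2 cell reads: "Hold until baseline. Treat symptomatically, and restart if improved to baseline or grade 1 at investigators discretion".

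**The concern.** A dose-delay cell is an operative instruction: whoever holds the protocol on a dosing day must be able to read one action from it. Here two investigators with the same patient and the same laboratory result can act differently, and each can point to a sentence in the cell.

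Three things depend on the reading chosen. The first is checkpoint-inhibitor exposure, because Section 6.1 says that doses missed during a hold are omitted. The second is the safety management of symptomatic pancreatitis, where one sentence removes the patient from treatment and another may let dosing go on. The third is the delay record, which feeds two removal rules in Section 6.1: off protocol therapy after more than two delays for the same event, and off study after a hold of more than 42 days. Safety and toxicity profile are part of the primary objective, so dosing after a toxicity should follow one rule.

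**Working it through.** The plan has no figure to reproduce on this point. The check compares sentences within the cell, and then looks for a rule elsewhere that settles the conflict.

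**Step 1: the two possible scopes of the last sentence.**

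| Scope of the last sentence | Patient | Earlier sentence | Last sentence | Result |
|---|---|---|---|---|
| Whole Grade 3 cell | Asymptomatic Grade 3 elevation | No dose until Grade 2 or lower | Dose may be given | Conflict |
| Its own bullet only | New symptomatic pancreatitis | Off nivolumab/ipilimumab | Dose may be given | Conflict |

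On either scope the sentence conflicts with an earlier one.

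**Step 2: search for a rule of precedence.** The opening of Section 6.1 sends patients who cannot resume back to the tables. Under the all-other-events table, the bullet on Grade 3 or 4 laboratory abnormalities ends "or that does not require treatment does not require discontinuation". It deals with discontinuation and does not choose between holding and continuing. Another bullet there tells the investigator to stop treatment that poses a substantial risk, but gives no licence to continue. None of these settles the cell.

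**Step 3: effect on exposure.** In cycles 1 to 4 of the triplet, nivolumab is due on days 8, 22 and 36 and ipilimumab on day 8 only. One omitted nivolumab visit is 1/3 of that cycle's nivolumab doses. A hold that causes the day 8 visit to be missed also removes 1/1 of that cycle's ipilimumab doses. The same event therefore gives different exposure according to the sentence followed, and it is logged as a delay under one reading and not under the other.

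**Step 4: effect on the cycle 1 DLT count.** Section 5.2.1 makes Grade 3 or higher non-hematologic toxicity dose limiting, with listed exceptions for fatigue, diarrhea, nausea and vomiting, creatinine, electrolytes and liver function tests. Amylase and lipase are not among them. A Grade 3 elevation judged at least possibly related is therefore a DLT whether dosing is held or continued. One judged unrelated is not a DLT under either sentence, because the definition requires attribution.

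**Step 5: the 42-day rule and cycle 1.** The first checkpoint-inhibitor dose is on day 8. A hold from day 8 first exceeds 42 days on day 8 + 42 = day 50, after cycle 1 ends on day 42. Even a hold counted from day 1 would reach exactly 42 days on day 42, and the rule requires more than 42. Section 5.1.2.1 states that DLTs after cycle 1 do not affect escalation.

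**Step 6: Grade 2 diarrhea.** With baseline Grade 0 and improvement to Grade 1, the first sentence keeps the hold and the second permits a restart. With baseline Grade 1, the two thresholds coincide. The wording conflicts only when baseline is below Grade 1.

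**Step 7: how many patients.** The nivolumab CAEPR in Section 7.1.2 lists increased lipase and increased amylase in its band of 20% or less, without a split by grade. No Grade 3 rate is given, so no count of affected patients can be derived.

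**The case against.** The best defence is that a graded scheme was intended: dosing continues at Grade 2, is discretionary at Grade 3, and is held at Grade 4. The Grade 2 and Grade 4 rows would fit that. But the Grade 3 cell's own opening sentence is an unqualified hold, and nothing marks the last sentence as an exception to it. The defence also fails if the last sentence belongs to the bullet in which it stands. The table further refers to the hepatic algorithm in Appendix C for treating symptomatic pancreatitis. That figure is not shown in the text available and cannot be checked, but it would not remove the conflicting sentences from the cell.

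On diarrhea, the objection largely stands. The second sentence reads naturally as a discretionary relaxation of the first, and it agrees with the general Grade 2 rule under all other events, which accepts Grade 1 or baseline. That is why this part is secondary.

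A reader might also infer more than the documents support:

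- **That the ambiguity changes the DLT rate used for escalation.** For amylase/lipase it does not (Step 4). A prolonged hold for either toxicity cannot reach the 42-day rule within cycle 1 (Step 5).
- **That the diarrhea table contains a third restart threshold.** The bullet on retreatment after resolution covers a defined subgroup, those with Grade 2 symptoms and a normal colonoscopy and biopsies. It is not a competing rule for all Grade 2 patients.
- **That Table 3 sizes the diarrhea problem.** Its 24.9% for low-grade GI events comes from ipilimumab 10 mg/kg, against 1 mg/kg here, and pools Grades 1 and 2. Section 2.1.2.4 adds that the nivolumab/ipilimumab combination raises the frequency and severity of most events. The figure is therefore neither an estimate nor a bound for this triplet.

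**Conclusion.** The Grade 3 amylase/lipase cell contradicts itself on either reading of its last sentence, and no other text in Section 6 resolves it. This is an inconsistency in a safety-relevant dosing rule. It is not a flaw in the escalation design, and the cycle 1 DLT count is unaffected. The size per event is one or more checkpoint-inhibitor doses given or omitted, and a delay counted or not counted towards removal. The number of patients is unknown. The conclusion rests on the text of the cell as it stands and on amylase and lipase lying outside the Section 5.2.1 exceptions. The Grade 2 diarrhea wording is a minor companion point, limited to patients whose baseline is below Grade 1.

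**What to change.** The sponsor's clinical team should reconcile the sentences in the Grade 3 amylase/lipase cell so that one instruction applies to asymptomatic Grade 3 elevation and one to symptomatic pancreatitis. If investigator discretion is meant to apply to either group, the cell should say to which. In the same amendment, the hold and restart wording in the Grade 2 diarrhea cell should be reconciled into one threshold. Which rule to adopt is a clinical decision, and this review takes no view on it.

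The cost is wording in two table cells, plus a check that the Appendix C algorithms agree with the result. Sample size, the escalation rule and the analysis do not change.

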Grade 3	Hold until ≤ Grade 1. Resume at same dose level.
Grade 4	Off treatment

Endocrine: Hypophysitis Adrenal Insufficiency	Management/Next Dose for Nivolumab and Combination Nivolumab/Ipilimumab
≤ Grade 1	Asymptomatic TSH elevation*. Patients must be evaluated, endocrine consult. May continue treatment at same dose level at investigator discretion.
Grade 2	Hold until patients are on a stable replacement hormone regimen and symptoms resolve. If treated with steroids, patients must be stable off steroids for two weeks. Resume at same dose level.
Grade 3	Hold until patients are on a stable replacement hormone regimen and symptoms resolve. If treated with steroids, patients must be stable off steroids for two weeks. Resume at same dose level.
Grade 4	Off nivolumab/Ipilimumab treatment.

\*Patients with thyroiditis may be retreated on replacement therapy. Patients must be evaluated to rule out pituitary disease prior to initiating thyroid replacement. Please evaluate pituitary function before beginning steroid therapy or replacement therapy of any kind.

Note all patients with symptomatic pituitary enlargement, exclusive of hormone deficiency, but including severe headache or enlarged pituitary on MRI should be considered grade 3 events. Isolated thyroid or testosterone deficiency may be treated as grade 2 if there are no other associated deficiencies and adrenal function is monitored.

Recommended management: See Endocrine Management Algorithm ([Appendix C](#))

Pneumonitis	Management/Next Dose for Nivolumab and Combination Nivolumab/Ipilimumab	Toxicity management
≤ Grade 1	
Hold dose pending evaluation and resolution to baseline including baseline pO2. Resume no change in dose after pulmonary and/or ID consultation excludes lymphocytic pneumonitis.
	
For Grade 1 (radiographic changes only):
 
 
- Monitor and closely follow up in 2-4 days for clinical symptoms, pulse oximetry (resting and exertion) and laboratory work-up and then as clinically indicated
 
- Consider pulmonary and infectious disease consult
 

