All Grades	
Distinguishing inflammatory pneumonitis is often a diagnosis of exclusion for patients who do not respond to antibiotics and have no causal organism identified including influenza. Most patients with respiratory failure or hypoxia will be treated with steroids. Patients who require steroids should be taken off nivolumab treatment. Bronchoscopy may be required and analysis of lavage fluid for lymphocytic predominance may be helpful. Patients with new lung nodules should be evaluated for sarcoid like granuloma.
 
The investigator is requested to differentiate between non-infectious pneumonitis, and infectious pneumonitis (viral, bacterial, or fungal), aspiration pneumonitis, or other pneumonitis clearly not due to a potential hypersensitivity reaction to the study agent infusions; and provide the basis for his/her assessment that it is infectious or other, as appropriate. The investigator is requested to report with the most specific clinical terms to describe the condition, not simple “pneumonitis”.
	

Additional guidance can be found in the Pulmonary Adverse Event Management Algorithm ([Appendix C](#)). Consider recommending seasonal influenza killed vaccine for all patients.

Fatigue	Management/Next Dose for Nivolumab and Combination Nivolumab/ipilimumab
$\leq$ Grade 1	Continue therapy. No change in dose.
Grade 2	Continue therapy. No change in dose.
Grade 3	Hold until $\leq$ Grade 2. Resume at same dose level.
Grade 4	Off nivolumab/ipilimumab therapy.

Fatigue is the most common adverse event associated with immune checkpoint therapy. Grade 2 or greater fatigue should be evaluated for associated or underlying organ involvement including pituitary, thyroid, and hepatic, or muscle (CPK) inflammation.

Neurologic events	Management/Next Dose for Nivolumab and Combination Nivolumab/ipilimumab
$\leq$ Grade 1	Hold dose pending evaluation and observation. Resume with no change in dose when resolved to baseline.
Grade 2	Hold dose pending evaluation and observation. Hold until baseline. Off protocol treatment if steroids are required. Resume at same dose level

Neurologic events	Management/Next Dose for Nivolumab and Combination Nivolumab/ipilimumab
	for peripheral isolated n. VII (Bell's palsy).
Grade 3	Off nivolumab/ipilimumab treatment.
Grade 4	Off nivolumab/ipilimumab treatment.
Patients who require steroids should be taken off nivolumab/ipilimumab treatment.	

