Patients with any CNS events including aseptic meningitis, encephalitis, symptomatic hypophysitis, or myopathy, peripheral demyelinating neuropathy, cranial neuropathy (other than peripheral n. VII), GB syndrome, myasthenia gravis should be off study.	
Recommended management: See Neurologic Adverse Event Management Algorithm (Appendix C)	

Infusion reaction	Management/Next Dose for Nivolumab and Combination Nivolumab/ipilimumab
≤ Grade 1	No change in dose.
Grade 2	Hold until ≤ Grade 1. Resume at same dose level.
Grade 3	Hold until ≤ Grade 1. Resume at same dose level with pre-medication at the discretion of the PI.
Grade 4	Off treatment
Patients with fever should be evaluated as clinically appropriate. Patients may experience isolated fever during infusion reactions or up to several days after infusion. Evaluation over the course of 1-2 weeks should be done for other autoimmune events that may present as fever.	
The following prophylactic premedications for future infusions: diphenhydramine 25-50 mg (or equivalent) and/or paracetamol 325 to 1000 mg (acetaminophen) at least 30 minutes before additional nivolumab/ipilimumab administrations.	

Fever	Management/Next Dose for Nivolumab and Combination Nivolumab/ipilimumab
≤ Grade 1	Continue therapy. Evaluate and continue at same dose level
Grade 2	Hold until ≤ Grade 1. Resume at same dose level.
Grade 3	Hold until ≤ Grade 1. Resume at same dose level.
Grade 4	Off nivolumab/ipilimumab therapy
Patients with fever should be evaluated as clinically appropriate. Patients may experience isolated fever during infusion reactions or up to several days after infusion. Evaluation over the course of 1-2 weeks should be done for other autoimmune events that may present as fever.	
See table above for Infusion Reactions .	

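### Section 6.1 gives opposite re-dosing instructions for Grade 3 symptomatic hypophysitis: resume at the same dose (endocrine table) or leave the study (neurologic table)

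*Combined protocol and SAP*

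**What the plan says.** Three places in Section 6.1 deal with this event.

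- **Endocrine table (Hypophysitis, Adrenal Insufficiency).** The note beneath it says that "symptomatic pituitary enlargement, exclusive of hormone deficiency, but including severe headache or enlarged pituitary on MRI should be considered grade 3 events". The Grade 3 row reads "Hold until patients are on a stable replacement hormone regimen and symptoms resolve", followed by "If treated with steroids, patients must be stable off steroids for two weeks. Resume at same dose level". Only the Grade 4 row stops the checkpoint inhibitors.
- **Neurologic events table.** The Grade 3 row is "Off nivolumab/ipilimumab treatment". A line under the rows adds "Patients who require steroids should be taken off nivolumab/ipilimumab treatment". The closing note then lists "Patients with any CNS events including aseptic meningitis, encephalitis, symptomatic hypophysitis, or myopathy" with several neuropathies, and its list ends "GB syndrome, myasthenia gravis should be off study". The note sets no grade limit.
- **All other events table.** A bullet assigns Grade 3 to "hypophysitis with symptoms of headache, visual or neurologic changes or radiologic evidence of pituitary enlargement and other CNS events". It does not say whether the endocrine or the neurologic table then applies.

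**The concern.** A patient with Grade 3 hypophysitis and severe headache or an enlarged pituitary fits both tables. The endocrine table brings that patient back to treatment at an unchanged dose, including after steroids once two weeks off them have passed. The neurologic note removes the patient from the study.

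What is at stake is re-exposure to two checkpoint inhibitors, plus rhIL-15 if still in the first four cycles, after a serious immune event. The decision would depend on which table the investigator opened, and either choice could later be called a protocol deviation. Hypophysitis is foreseeable here: the CAEPR lists for both ipilimumab and nivolumab place it in the middle frequency column (up to 20%), not among the rare events. Section 3.2.1 also does not bar patients who had a Grade 3 or higher endocrinopathy on an earlier checkpoint inhibitor.

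**Working it through.** The plan states no figure to reproduce. The check sets the rules side by side and then asks whether the resume path can actually be reached.

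**1. Same event, two rules**

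| Step | Endocrine table | Neurologic table and note |
|---|---|---|
| Is the event covered? | Yes: the heading names hypophysitis and the note covers symptomatic enlargement | Yes: the closing note names symptomatic hypophysitis |
| Grade | 3, by its own note | Note applies at any grade |
| Action | Hold, then resume at same dose | Off study |
| If steroids were used | Resume after two weeks stable off them | Off nivolumab/ipilimumab |

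The first three rows carry the contradiction. The neurologic table's Grade 3 row and steroid rule apply only once the event is treated as neurologic, so they support the point but do not add separate contradictions.

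**2. Is there a rule of precedence?**

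- The All other events table grades the event but names no governing table. Its own Grade 3 rule for immune-related events is hold and resume, subject to exceptions in the later tables, which leads back to the conflict.
- The Appendix C preamble allows resumption for patients found not to need steroids for an autoimmune event. It does not cover those who do need them.
- The visible text of the endocrinopathy algorithm mentions visual field testing and imaging, so it does not confine itself to hormone deficiency. The Appendix C flowcharts are not shown and nothing is assumed about them.
- Elsewhere the protocol does write such rules. Overlapping SPEER lists use the lower grade, and a footnote to the cardiac table sends myositis without myocarditis to the All other events rules. Nothing similar appears here.

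**3. Can the resume path be reached?**

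Inputs: 42-day cycles, nivolumab on days 8, 22 and 36, ipilimumab on day 8 (Section 5, triplet treatment plan); off study if treatment is held more than 42 days (Section 6.1).

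- Cycle 2 day 8, on schedule, is day 42 + 8 = 50.
- Hold starting at the cycle 1 day 22 dose: 50 − 22 = 28 days, inside the cap.
- Counted from the last dose given, on day 8: 50 − 8 = 42 days, still not more than 42.

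**4. Size of the contrast for one such patient, cycles 2 to 4**

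- Endocrine table: nivolumab 3 doses × 3 cycles = 9; ipilimumab 1 dose × 3 cycles = 3.
- Neurologic note: 0 and 0.

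**5. DLT count**

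Section 5.2.1 makes Grade 3 or higher non-hematologic toxicity dose limiting and lists no endocrine exception. A treatment-related Grade 3 event in cycle 1 therefore counts under either table.

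**The case against.** The strongest counter-argument is that a consistent reading exists. The bullet in the All other events table speaks of hypophysitis with headache, visual or neurologic change or enlargement together with *other* CNS events, which classes that presentation as a CNS event, the category the neurologic note takes off study. The endocrine Grade 3 row asks for stable hormone replacement, which fits poorly with a patient who has no deficiency, and the endocrine note only assigns a grade. On this reading, deficiency belongs to the endocrine table and mass effect to the neurologic one.

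This has some force as a guide to what was intended, but it does not settle what is written. The endocrine note puts enlargement without deficiency under the endocrine table, where the Grade 3 row is the only Grade 3 instruction. A patient with both enlargement and deficiency meets both rules on any reading.

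The second argument is that few patients would reach the resume path. That stands in part. In the 28-day example, a patient given steroids has 28 − 14 = 14 days for the course and taper; even at the 42-day cap it is 42 − 14 = 28 days. Table 3 gives a median resolution time of 20.1 weeks (20.1 × 7 ≈ 141 days) for Grade 2 to 4 endocrine events. That figure comes from ipilimumab 10 mg/kg, not the 1 mg/kg used here, and covers all endocrine events. The rule here asks for resolved symptoms on stable replacement, which is not necessarily what the table measured. It suggests that some holds will exceed the cap, not that all will.

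The third is that safeguards exist: resumption is conditional, the investigator may stop for substantial risk, and Section 12.1 has each patient discussed weekly. These limit harm, but none says which rule applies.

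**Conclusion.** The concern holds. Section 6.1 contains two explicit and opposite instructions for Grade 3 symptomatic hypophysitis, and no visible text ranks them. Severity is minor to moderate. The consequence is inconsistent re-dosing after a serious immune event; dose escalation, the MTD rule and the sample size are essentially untouched.

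The per-patient contrast of 9 nivolumab and 3 ipilimumab doses against none is a maximum. It assumes onset early enough for the hold to begin by cycle 1 day 22, restart on cycle 2 day 8, an on-schedule cycle 2 and no later interruption through cycle 4. No expected number of patients is given, because the documents report no rate of symptomatic hypophysitis at ipilimumab 1 mg/kg. At Grade 2 a conflict arises only if symptomatic hypophysitis is taken to include symptoms of hormone deficiency; that is secondary. A flowchart in Appendix C might favor one path, but the two tables would still disagree.

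**What to change.** Amend Section 6.1 so that one rule applies. The sponsor's safety physicians should choose between:

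- **Option A (hold and resume).** Remove symptomatic hypophysitis from the off-study list in the neurologic note, refer the reader to the endocrine table, and state that the neurologic steroid stop rule does not apply to this event.
- **Option B (stop).** Change the endocrine Grade 3 row and note so that symptomatic pituitary enlargement or a CNS presentation means stopping nivolumab and ipilimumab. Keep hold-and-resume for hormone deficiency controlled on replacement.

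Option B fits better with the existing neurologic note and with the bullet in the All other events table that groups this presentation with CNS events. If it is chosen, the text should also say whether the patient leaves the study or only stops the checkpoint inhibitors, since the neurologic row and note differ on that. Whichever is chosen, the Appendix C algorithms should be checked for agreement.

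The cost is a wording amendment, with no added patients, visits or tests.
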